Official Title: The Value of Home Chlorhexidine Pre-Surgical Wash before Spine Surgery

NCT Number: NCT02767427

PI: [name] [name]

Site: Columbia University Irving Medical Center

Version: 07/02/2018

Study Purpose and Rationale:

Surgical site infections lead to significant morbidity and mortality. These complications lead to severe clinical, and economic, burdens across surgical disciplines, and may have especially harmful consequences in spine surgery, where they can lead to extensive revision surgeries as well as neurologic sequelae, or even death.

Other trials have examined the effects of presurgical cleansing with chlorhexidine with mixed results. For example, Murray et al. performed a prospective, randomized study examining the effect of CHG cloth treatment at home preoperatively (1). Their study, which was industry sponsored, concluded that pre-cleansing led to decreased bacterial culture positivity preoperatively. However, they reported only on the results of their sample taken in the preoperative holding area. The most relevant data is arguably the bacterial burden after preoperative prep, to determine whether the level equalizes in both groups after the chlorhexidine is applied immediately preoperatively. Additionally, they looked at its use before shoulder surgery, while we are looking at the effects prior to spine surgery.

Another study by Ng et al. prospectively studied the effect of chlorhexidine foot washes on patients prior to foot and ankle surgery and found reductions in bacterial burden after washing (2). They analyzed bacterial flora qualitatively rather than quantitatively, reporting only culture positivity rather than bacterial colony counts. They claim that CHG decreased flora intraoperatively, however their "intraoperative" sample took place after washing and before prep and drape; it could more precisely be labeled a preoperative sample. It was taken about twenty minutes after washing, so it is not surprising that the burden was decreased in this actually preoperative sample. There was a reduction postoperatively in the chlorhexidine footbath group. However, this was not statistically significant.

Significant effort has been put forth by surgeons in the past few decades to decrease the rate of surgical site infections. One intervention has been the adoption of chlorhexidine use by the patient at home preoperatively. There has been conflicting evidence about its potential efficacy in decreasing bacterial loads and infection rates across surgical populations. This intervention has been a subject of numerous trials and reviews over the last several years and has recently been a topic of interest in the orthopedic surgery literature as well. However, no prior study has analyzed the benefit of such an intervention with regards to the field of spine surgery.

Scientific Abstract:

To our knowledge no prior study has evaluated the effects of preoperative skin cleansing on the cutaneous bacterial burden for patients undergoing spine surgery. Surgeons use various methods to decrease the risk of infection in patients perioperatively. We would like to conclusively determine whether or not at-home preoperative skin cleansing with chlorhexidine decreases the bacterial burden pre-operatively for patients undergoing spine surgery, and if these effects are eliminated after the pre-surgical chlorhexidine prep. We will perform a prospective, randomized clinical trial to assess the impact of home chlorhexidine wipes and evaluate whether this intervention leads to a change in bacterial counts on patients pre- and intra-operatively. Validating their efficacy will allow optimal protocols to be

designed that contribute to improved outcomes without adding undue mental or financial burden on patients.

Lay Abstract:

To our knowledge no prior study has evaluated the effects of cleaning the skin at home before surgery in patients undergoing spine surgery. We will perform a clinical trial to see if patients who use the chlorhexidine cleansing wipe have decreased amounts of bacteria on their skin when they arrive for their scheduled spine surgery. Spine surgeons strive to decrease infections in their patients, so it is important to see if this intervention helps to do this.

Research Question/Hypothesis:

We plan to assess the effect of preoperative chlorhexidine skin cleansing on cutaneous bacterial loads.

1. We hypothesize that preoperative washing will decrease overall bacterial burden upon patient arrival to the pre-operative holding area and before the pre-surgical prep.
2. We also believe that the immediate pre-operative and the intra-operative bacterial counts will be unaffected by this intervention.

Study Design:

We will perform a prospective, randomized clinical trial at Columbia University, specifically the Allen Pavilion as our test site.

Clinical Trial:

We will prospectively analyze 40 patients undergoing spine procedures at Columbia University. After attaining IRB approval, and confirming that all surgeons included in this study will abide by the standardized preoperative protocol, we will begin trial enrollment.

Patients undergoing spine surgery will be included after informed consent with the surgical team during their preoperative clinical evaluation. Randomization will occur through use of numbered envelopes with cards inside with detailed instructions for patients in the chlorhexidine versus placebo groups; grouping will be determined by a random number generator matching to the envelope numbers. The attending surgeon, as well as the microbiology lab analyzing the sample, will be blinded to the selected intervention.

Inclusion Criteria:

- 18 years old or older
- Scheduled for elective spine surgery at Columbia University Medical Center

Exclusion Criteria:

- Unable to apply at-home chlorhexidine wipe by themselves
- Deemed "high risk" preoperatively by the treating surgeon
- Diagnosed with spine trauma
- Undergoing deformity correction surgery
- Unable to consent to the terms of the surgery
- Known infection at time of the index procedure
- Hospitalized within 1 week pre-operatively
- Allergic to chlorhexidine
- Immunocompromised
- End stage renal disease on dialysis

- Local or systemic skin disease (such as psoriasis, eczema, etc.)
- Open skin wounds

Patient Criteria

Adult patients 18 years of age and older who are undergoing elective primary spine surgery will be included in the surgery. Patients included in the study also will agree to perform the intervention of washing their surgical site by themselves (rather than through the help of an assistant). Patients who are deemed “high risk” preoperatively by the treating surgeon, as well as spine trauma patients and those undergoing deformity correction surgery, will be excluded from this study. Patients will also be excluded if they are unable to consent to the terms of the study, or if they are physically unable to wash their surgical site due to physical constraints, e.g., shoulder pathology that prohibit them from reaching the site of their spine surgery. Patients will be excluded if they had known infection at time of the index procedure, hospitalized within 1 week pre-operatively, or are known to have allergies to chlorhexidine. Patients will also be excluded if they had immune compromise, end stage renal disease on dialysis, local or systemic skin disease (such as psoriasis, eczema) or open skin wounds.

Data will be collected for patients regarding demographic variables such as age, gender, race, BMI, as well as compliance with cleansing protocol (washed once, twice, or not at all), occurrences of side effects from cleansing, whether they had shaved their surgical site or needed shaving in the OR, and presence of diabetes, rheumatoid arthritis, or chronic renal insufficiency, as well as other comorbid medical conditions.

Intervention

Patients will be randomized to the chlorhexidine or no additional intervention groups. Patients will be randomized to use 4% chlorhexidine cloths, while the other half receive no additional intervention. Those randomized into the CHG home-application group will be asked to shower the night before surgery, and to use a standardized pre-packaged chlorhexidine gluconate wipe (that they would receive at their pre-surgical consultation) on their surgical site after thoroughly drying those areas. They will be asked to use a second wipe in each area the morning of surgery. Those who forget to use the wipe in the morning are allowed to use the wipe in the pre-operative area and included if this occurs more than one hour before skin prep. The surgical sites will be analyzed in two groups: anterior cervical and posterior spine. Each of these two groups will be randomized separately. All patients will undergo a standardized preoperative cleansing regimen. Once positioned, they will be cleansed with an alcohol solution. Then, the surgical site (either the anterior portion of the neck or the posterior area of the spine) will be scrubbed with chlorhexidine-soaked brushes and then painted with chlorhexidine solution. Perioperative antibiotics will be given per attending surgeon preference.

Specimen Sampling

Cutaneous samples will be taken from the surgical site of each patient at each time point. Initial skin sample would be taken in the office at the preoperative clinical visit at time of booking. The next specimen will be acquired pre-operatively after the patient is positioned on the operating table, before the skin prep. A third sampling occurs immediately before draping, after the skin prep had been given adequate time to completely dry. The fourth sample will be taken 1hr after the start of the case from superficial subcutaneous tissue. All specimens were taken by a sterile BD E-Swab, which will be rubbed 10 times (five times in one direction, five times in the other) lightly along a 5cm site the surface of the site being used for the incision. This swab will be then placed in the ESwab collection system. All samples will be sent immediately after acquisition to the microbiology lab for analysis within twenty-four hours.

Statistical Procedures:

Data will be analyzed in intent-to-treat manner. All patients will be asked in the preoperative holding area about their compliance to the home cleansing regimen. Those who are noncompliant or only partially compliant with their treatment will still be included in the intent-to-treat analysis and will also be removed for subsequent analysis of only patients who were fully compliant with treatment. Power analysis will be performed before the start of the trial in order to achieve adequate power to detect significant decreases in the bacterial burden after intervention. The standard deviation of the data will be assessed after the pilot trial so that this calculation can be performed. Data analysis will be done through multivariate analysis with logistic regression and chi squared analysis, using SPSS.

Recruitment:

Patients will be enrolled prospectively as they present to the medical practice of the spine practice. If they are eligible based on inclusion criteria and exclusion criteria, they will be offered informed consent and enrollment into the trial. Only patients who present to the offices of the spine attendings included in the study and who are eligible will be identified and the study discussed with them. Pilot trial patients will be recruited from word-of-mouth discussion with study investigators and healthcare staff within Columbia.

Potential Benefits:

Patients undergoing adult spine surgery at CUMC do not currently receive at-home chlorhexidine wipes. They are an additional anti-microbial measure that possibly decrease the amount of bacteria on the skin. Through this trial, half of the enrollees will obtain this additional potentially anti-microbial step in their preoperative regimen, which could potentially decrease their risk of developing surgical site infections.

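### The plan expects no effect of the wipe after the skin prep but gives no criterion for concluding it; as written, the only support would be a non-significant difference test

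*Combined protocol and SAP*

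**What the plan says.** Three places put a no-effect question to the samples taken after the skin prep.

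- **Study Purpose and Rationale** faults an earlier trial for reporting only its holding-area sample. It calls the post-prep burden arguably the most relevant data, "to determine whether the level equalizes in both groups after the chlorhexidine is applied immediately preoperatively".
- **Scientific Abstract**: "We would like to conclusively determine whether or not at-home preoperative skin cleansing with chlorhexidine decreases the bacterial burden pre-operatively" in spine surgery patients, and "if these effects are eliminated after the pre-surgical chlorhexidine prep". The next sentence adds a difference question, to "evaluate whether this intervention leads to a change in bacterial counts on patients pre- and intra-operatively".
- **Research Question/Hypothesis**, item 2: "We also believe that the immediate pre-operative and the intra-operative bacterial counts will be unaffected by this intervention".

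Specimen Sampling defines four samples. On the third: "A third sampling occurs immediately before draping, after the skin prep had been given adequate time to completely dry". The fourth is taken from superficial subcutaneous tissue one hour into the case. That section does not use the label 'immediate pre-operative'. I take hypothesis 2 to refer to samples 3 and 4, which is an inference, though a natural one.

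Statistical Procedures is the only statistical section. It gives an intent-to-treat analysis, a further analysis of fully compliant patients, a power analysis still to be done and aimed at detecting decreases, and logistic regression with chi-squared tests. It states no alpha, margin, interval rule or other way of judging that an effect is absent.

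**The concern.** A test of difference can reject equality but cannot establish it. Hypothesis 1 predicts a decrease on arrival, so a difference test suits it. Hypothesis 2 predicts no effect, and the same tests can only contradict it or fail to contradict it. Failing to contradict it is also what a small sample produces when a real difference exists.

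At stake is the comparison that the rationale ranks highest. A non-significant result at samples 3 and 4 could be reported as showing that the prep removes any benefit of the home wipe, while the data still allowed a sizeable residual difference.

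**Working it through.** **Inputs from the documents.** Total sample size is 40 (Clinical Trial). Half receive the wipe (Potential Benefits), so 20 per arm if exactly balanced. There are two site groups, randomized separately (Intervention): "The surgical sites will be analyzed in two groups: anterior cervical and posterior spine".

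**Not in the documents.** Alpha, power, effect size, SD, post-prep positivity and any margin. The figure of 40 therefore cannot be reproduced.

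**Assumptions.** Two-sided 0.05, all samples obtained, culture positivity as the outcome, and the rates shown. These are illustrations, not estimates.

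**1. How often a real difference gives a non-significant result.** With a and b positives among n per arm and t = a + b, the uncorrected statistic is X² = (a - b)² × 2n / [t(2n - t)]. Summing the binomial probabilities of all tables with p of at least 0.05, for n = 20:

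| True positivity | Probability of non-significance |
|---|---|
| 30% v 10% | 0.643 |
| 20% v 5% | 0.708 |
| 30% v 5% | 0.409 |

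**2. What a non-significant table leaves open.** Take 3/20 v 0/20.

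- X² = 9 × 40 / (3 × 37) = 360/111 = 3.24, p = 0.072.
- Wilson 95% limits: 0.052 to 0.360 for 3/20, and 0 to 0.161 for 0/20.
- Newcombe lower limit: 0.15 - √[(0.15 - 0.052)² + (0.161 - 0)²] = 0.15 - 0.188 = -0.038.
- Newcombe upper limit: 0.15 + √[(0.360 - 0.15)² + 0²] = 0.360.

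The result is non-significant, yet the interval runs from -4 to +36 percentage points. Likewise 6/20 v 2/20 gives X² = 16 × 40 / (8 × 32) = 2.50, p = 0.114, with an interval of -5 to +43 points.

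**3. The most favourable table.** For 0/20 v 0/20 each Wilson upper limit is z²/(n + z²) = 3.84/23.84 = 0.161, so the Newcombe interval is about ±16 points. Within one site group, assuming an even split (10 per arm), 0/10 v 0/10 leaves 3.84/13.84 = 0.278, about ±28 points.

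**4. Whether the planned logistic model fills the gap.** It can supply an interval, but when one arm has no positives there is no finite unadjusted odds ratio. With common positivity p, the chance that at least one arm has none is 1 - [1 - (1 - p)^20]². This is 0.588 at p = 5%, 0.228 at 10% and 0.002 at 30%. If the prep leaves few positive cultures, the interval may be unusable where it is most needed.

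**5. Counts.** I attach no figure. The precision of a count comparison with many zeros depends on how many samples are positive and how variable the positive counts are, and the documents give neither.

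**The case against.** The commitment is soft. The abstract says what the investigators would like to determine. Item 1 is hypothesized, whereas item 2 is only believed. The Lay Abstract mentions only the arrival question, and the abstract's statement of what the trial will evaluate asks about a change, which difference tests address. Hypothesis 2 can thus be read as an expectation and not an equivalence objective. This has some force and is why labelling it exploratory is an acceptable remedy. It does not remove the point: item 2 is a numbered hypothesis, the abstract's sentence carries through to whether effects are eliminated, and the rationale gives that comparison priority.

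The harm is also conditional. A reader might infer that the plan will treat non-significance as proof of no effect. It does not say so; the risk lies in reporting. Nor are the chosen tests wrong in themselves, since they suit the difference question. What is missing is a decision rule, not every means of estimation.

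The rates are assumed. Nothing in the documents supports 30% positivity after alcohol, chlorhexidine scrub and paint. That is fair, and the point does not rest on those rates: even with no positive culture in either arm, step 3 shows that a range of differences remains open.

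Finally, a reader might think that the abstract's hope of designing optimal protocols depends on a no-effect finding. The abstract ties that hope to validating efficacy, so I give it no weight here.

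**Conclusion.** The concern stands as an omission that should be fixed. The documents ask whether the wipe's effect disappears after the prep and provide only tests that cannot answer yes. This follows from the text alone and needs none of the assumed numbers.

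The size is illustrative, under 20 per arm and two-sided 0.05: roughly 41% to 71% of the assumed true differences would go undetected, and non-significant tables can leave differences of more than 35 percentage points open. A reader might go further and infer that hypothesis 2 cannot be settled with 40 patients. The documents do not support that. The answer depends on post-prep positivity, count variability and the margin chosen, none of which is given. Hypothesis 1 is untouched.

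**What to change.** Add to Statistical Procedures:

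- At samples 3 and 4, report the between-arm difference with a 95% confidence interval: Newcombe or exact for positivity, and a method suited to many zeros for counts.
- Report a non-significant result as no difference detected. Do not describe the counts as unaffected or the effect as eliminated unless the interval lies inside a margin on an absolute scale (percentage points or log10 count) fixed before any between-arm outcome data are seen.
- If a margin is set, state whether the rule uses a 95% interval (2.5% per side) or a 90% interval (5% per side, easier to meet). State also whether it applies to counts, positivity or both, whether both samples must meet it, and whether the two site groups are pooled.
- If no margin is set, label hypothesis 2 exploratory.

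The cost is a few sentences. No margin is compulsory, and no extra patients or change to treatment or sampling is needed. The downside is that hypothesis 2 may be reported as inconclusive or exploratory; how likely that is cannot be judged from the documents.

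### The plan describes no step that inactivates chlorhexidine carried over on the swab, so at sample 2 killing in the tube could be counted as killing on the skin, in the wiped arm only

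*Combined protocol and SAP*

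**What the plan says.** **Exposure before the second sample (Intervention).** Allocation is described as "Patients will be randomized to use 4% chlorhexidine cloths, while the other half receive no additional intervention". The intervention arm wipes the site after showering the night before surgery, and then "They will be asked to use a second wipe in each area the morning of surgery". Patients who forget the morning wipe "are allowed to use the wipe in the pre-operative area and included if this occurs more than one hour before skin prep". No rinse after wiping is described.

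**Second sample (Specimen Sampling).** "The next specimen will be acquired pre-operatively after the patient is positioned on the operating table, before the skin prep".

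**Third sample.** It is taken once the prep has dried and before draping. By then the site in both arms has been cleansed with alcohol and "will be scrubbed with chlorhexidine-soaked brushes and then painted with chlorhexidine solution".

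**Handling.** The swab is rubbed ten times over the incision site. "This swab will be then placed in the ESwab collection system". The last instruction is "All samples will be sent immediately after acquisition to the microbiology lab for analysis within twenty-four hours". The document does not describe the tube medium, diluent, plating medium, counting method, any recovery control, or any record of the time from collection to plating.

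**Use of the result (Research Question/Hypothesis).** Hypothesis 1 reads "We hypothesize that preoperative washing will decrease overall bacterial burden upon patient arrival to the pre-operative holding area and before the pre-surgical prep". Hypothesis 2 predicts that the home wash leaves the later counts unaffected.

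**The concern.** The trial measures bacteria recovered in the laboratory and reads them as bacteria on the skin. The two agree only if nothing kills organisms between swabbing and plating. A swab drawn over recently wiped skin may collect antiseptic along with the bacteria, and both then share a tube until the specimen is processed.

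This would be a bias and not just noise, because at the second sample only one arm has had study chlorhexidine. Any carry-over lowers recovery in that arm alone, in the direction hypothesis 1 predicts. The design's usual protections do not reach it:

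- Randomisation does not help, because the error is a consequence of the assigned treatment.
- Blinding the laboratory does not help, because the agent travels with the specimen.
- The office baseline swab precedes any exposure.
- More patients would make a spurious difference more significant, not smaller.

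At the third sample both arms have had the chlorhexidine prep. Carry-over there could add to the prep's true effect, lower both counts and help mask a difference, which would favour hypothesis 2.

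**Working it through.** The plan gives no figure for carry-over, SD, alpha or effect size, so there is none to reproduce. The check has two parts.

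**1. Study chlorhexidine exposure by arm and sample**

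| Sample | Intervention arm | Control arm |
|---|---|---|
| 1, office visit | none | none |
| 2, positioned, before skin prep | two wipes, the second that morning or little more than an hour before prep | none |
| 3, after prep has dried | wipes plus scrub and paint | scrub and paint |
| 4, subcutaneous, 1 hour into the case | as sample 3 | as sample 3 |

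The imbalance is at sample 2. Two ambiguities do not remove it. The Clinical Trial section calls the comparator a placebo group while Intervention gives it nothing extra, but neither says controls receive chlorhexidine. The alcohol cleanse also happens once the patient is positioned, so its order relative to sample 2 is unclear, but it applies to both arms.

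**2. Sensitivity of the sample 2 comparison**

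Observed difference = true skin difference + in-tube loss in the wiped arm.

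From the document: 40 patients, half per arm, so 20 per arm. Assumed: true skin difference 0, two-sided alpha 5%, SD 1 log10, t-test on log10 counts, and a loss *d* of 0.25 to 1.0 log10. The chance of significance is the power of the two-sample t-test with noncentrality

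δ = (d / SD) × √(n/2), on 2n − 2 degrees of freedom.

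For n = 20, √(20/2) = 3.162 and the critical value on 38 df is 2.024. For n = 10, √(10/2) = 2.236 and the critical value on 18 df is 2.101. The n = 10 column reflects the plan to analyse anterior cervical and posterior sites as two groups, and assumes an even split (40 / 2 sites / 2 arms).

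| In-tube loss (log10) | δ, n = 20 | Chance of p < 0.05, n = 20 | δ, n = 10 | Chance of p < 0.05, n = 10 |
|---|---|---|---|---|
| 0.25 | 0.79 | 0.120 | 0.56 | 0.083 |
| 0.50 | 1.58 | 0.338 | 1.12 | 0.185 |
| 0.75 | 2.37 | 0.637 | 1.68 | 0.355 |
| 1.00 | 3.16 | 0.869 | 2.24 | 0.562 |

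The result depends heavily on the SD. For a 0.5 log10 loss at 20 per arm it is 0.869 with SD 0.5 and 0.177 with SD 1.5.

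**Binary version.** Statistical Procedures names logistic regression and chi-squared, so the outcome may be culture positivity. If log10 counts are normal with SD 1 and mean *m* above the detection limit, the positive share is Φ(m) in controls and Φ(m − d) in the wiped arm. Summing exact binomial probabilities over all outcomes in which the uncorrected chi-squared test is significant, 20 per arm:

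| m (log10) | Control share | d = 0.25: share, chance | d = 0.5: share, chance | d = 1.0: share, chance |
|---|---|---|---|---|
| 2 | 0.977 | 0.960, 0.5% | 0.933, 2.6% | 0.841, 27% |
| 1 | 0.841 | 0.773, 8% | 0.691, 20% | 0.500, 67% |
| 0 | 0.500 | 0.401, 9% | 0.309, 23% | 0.159, 67% |

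Where most specimens are far above detection, a small loss does almost nothing to positivity. Nearer the limit it matters about as much as in mid-range rows of the t-test table.

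**The case against.** The strongest reply is that silence is not absence. The protocol's account stops when the specimen goes to the laboratory; it describes no laboratory method at all, nor the tube's contents. The laboratory may already use a neutralising medium. A reader might infer that specimens are known to go unneutralised. The document does not support that, only that no such step is described. This stands, and the point is worded accordingly.

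Nor does the document show that residue persists on the skin until sampling, transfers in active amounts, or stays active in the tube. Twenty-four hours is a maximum; specimens are sent immediately. This also stands: the mechanism is possible and its size unknown.

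A reader might take 12% to 87% as the trial's false positive rate. It is not: those figures are the power of a test the plan does not name, at shifts chosen for illustration. The zero-effect scenario is also strained, since residue strong enough to kill in the tube has probably done something on the skin. An exaggerated effect is more likely than an invented one.

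A reader might also infer that low counts at sample 3 would be an artefact. Alcohol, scrub and paint may truly bring counts near zero, and a neutraliser would not change that. Carry-over could only add to it. Sample 4 comes from subcutaneous tissue, where carry-over is less clear, and nothing here rests on it.

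None of this removes the asymmetry at sample 2. If carry-over occurs, it acts on one arm, in the hypothesised direction, and cannot be separated from the wipe's effect once unneutralised specimens have been plated.

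**Conclusion.** The point holds as an unaddressed route to bias, not as a demonstrated one. The plan should say whether and where chlorhexidine is inactivated; as written, a lower sample 2 count in the wiped arm could reflect killing on the skin, killing in the tube, or both. That matters because the Scientific Abstract aims at a conclusive answer on bacterial burden.

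Under the stated assumptions, a loss of 0.25 to 1.0 log10 would yield significance in 12% to 87% of trials at 20 per arm, and 8% to 56% at 10 per arm within a site group. On culture positivity the range runs from under 1% to 67%, depending on how far counts sit above detection. The width of these ranges shows that the size cannot be judged from the document. If the tube or plating medium already inactivates chlorhexidine, a sentence saying so settles most of the concern.

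**What to change.** In Specimen Sampling:

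- Require that, after collection, every swab goes into a transport medium containing a chlorhexidine neutraliser, or is plated on neutralising medium within a fixed short time. Handle specimens identically in both arms and at all time points. If the existing medium already neutralises, say so.
- Record the collection-to-plating time for each specimen.
- If neutralisation cannot be confirmed, state that sample 2 and 3 counts may overstate the effect on the skin.

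The neutraliser belongs in the tube or on the plate. It should not reach the patient through pre-moistened swabs, since sample 3 is taken along the prepped incision line and sample 4 in the open wound.

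A bench recovery check would be useful but is optional: add a known inoculum to tubes holding swabs from wiped and unwiped skin, and compare recovery at 0 and 24 hours. It could sit alongside the planned pilot, but it is new work, because the pilot's stated purpose is to estimate the SD.

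The cost of the required changes is a different consumable, one extra recorded time, and possibly some dilution of low counts. They need no extra patients, visits or patient procedures.

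### The fully-compliant analysis can drop patients from the chlorhexidine arm only, so it is not a randomised comparison and is open to selection bias

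*Combined protocol and SAP*

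**What the plan says.** The Statistical Procedures section opens with "Data will be analyzed in intent-to-treat manner". It keeps noncompliant and partly compliant patients in that analysis, then says that they "will also be removed for subsequent analysis of only patients who were fully compliant with treatment". Compliance is taken from the patient's own report after randomisation: "All patients will be asked in the preoperative holding area about their compliance to the home cleansing regimen". The Patient Criteria section lists the categories as one wash, two washes or none, and gives no meaning for a control patient.

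The Intervention section describes the comparator twice: "Patients will be randomized to the chlorhexidine or no additional intervention groups" and "Patients will be randomized to use 4% chlorhexidine cloths, while the other half receive no additional intervention". Only the chlorhexidine group is asked to shower the night before and to use a wipe that night and again in the morning.

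One phrase points the other way. The Clinical Trial section, on randomisation, mentions "cards inside with detailed instructions for patients in the chlorhexidine versus placebo groups". No placebo product or placebo routine is described anywhere.

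**The concern.** Randomisation puts patients who would skip a wipe into both arms in equal expected numbers. Under the control condition in the Intervention section, skipping can be seen, and acted on, in one arm only. The second analysis therefore sets chlorhexidine patients who followed instructions against a control arm that still contains its would-be skippers. If people who follow washing instructions also tend to carry fewer skin bacteria, the wipes will appear to work even when they do nothing.

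The question behind this analysis, what the home regimen does when it is used, is a sensible one. The plan does not label the second analysis supportive, says nothing about how controls enter it, and gives no adjustment for selection. A favourable compliant-only result could then be read as evidence of efficacy beside a null ITT result.

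**Working it through.** **Inputs from the documents.** Total size: "We will prospectively analyze 40 patients undergoing spine procedures at Columbia University". Half go to each group, so about 20 v 20, ignoring the separate randomisation of anterior cervical and posterior cases. No alpha, power, SD, effect size or expected compliance is given, so the figure of 40 cannot be reproduced.

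**Inputs assumed.** No true effect; two-sided 5% t-test; a continuous outcome in SD units; a share p of patients who would be fully compliant; a correlation rho between tendency to comply and lower bacterial load. The plan names logistic regression and chi-squared, so these results show the mechanism and its rough size. They do not predict the plan's own test.

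**Formula.** If a compliant patient is one whose normally distributed tendency to comply lies in the upper share p, then with no wipe effect the expected difference, compliant chlorhexidine minus all controls, is

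bias = -rho × phi(z_p) / p,

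where phi is the normal density and z_p the normal quantile of p.

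- p = 0.90: phi/p = 0.1755/0.90 = 0.195. Times 0.3 gives -0.06 SD; times 0.5 gives -0.10 SD.
- p = 0.70: phi/p = 0.3477/0.70 = 0.497. Times 0.3 gives -0.15 SD; times 0.5 gives -0.25 SD.
- p = 0.60: phi/p = 0.3863/0.60 = 0.644. Times 0.5 gives -0.32 SD.

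**False-positive rates**, from 200,000 simulated trials per setting:

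| Share compliant | Correlation | Bias (SD) | False positives |
|---|---|---|---|
| 90% or 70% | 0 | 0 | 5.0% |
| 90% | 0.3 | -0.06 | 5.3% |
| 90% | 0.5 | -0.10 | 6.0% |
| 70% | 0.3 | -0.15 | 6.9% |
| 70% | 0.5 | -0.25 | 10.5% |
| 60% | 0.5 | -0.32 | 13.4% |

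Other runs put the two non-zero 90% rows as high as 5.6% and 6.1%, which changes nothing of substance. ITT on the same simulated data had a bias of about 0 and about 5% false positives throughout. The excess falls on one side: at 70% and 0.5, 10.2 of the 10.5 percentage points favour chlorhexidine, against a nominal 2.5.

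**Second model as a check.** Let noncompliers be a share q of each arm, with mean load d SD above that of compliers. The bias is then -q × d. For q = 20% and d = 1.0 this is -0.20 SD, with 7.9% false positives in 40,000 trials. For q = 10% and d = 0.5 it is -0.05 SD, with 5.2%. With d = 0 the bias is zero. Both models agree on mechanism and rough size.

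**The case against.** The strongest case against the point has four parts.

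*Bias is possible, not shown.* This stands. A reader might infer that the compliant-only analysis is biased as a matter of fact. The documents do not support that, because nothing in them relates compliance to bacterial load. With no relation there is no bias, and the opposite relation would reverse its sign.

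*Compliance may be high.* This stands as a limit on size. The trial enrols only patients who agree to wash themselves, excludes those physically unable to, and lets a forgotten morning wipe be used in the pre-operative area. At 90% compliance the distortion is small. The documents give no rate, so the whole range has to be shown.

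*Controls might have something to comply with.* The placebo wording and the statement that all patients are asked about compliance leave some doubt, so a reader should not conclude that one-arm removal is beyond dispute. The Intervention section is nevertheless explicit, twice, and no placebo routine is described. Even a real placebo would not rescue the analysis, since selecting on compliance after randomisation is not protected by randomisation.

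*ITT comes first.* This stands. A reader might infer that the trial's main result is compromised. It is not: ITT keeps every noncomplier, and the other analysis is described as subsequent. What remains is that the second analysis, as written, cannot answer the question it is there to answer.

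**Conclusion.** The point holds in a limited form. Under the untreated control of the Intervention section, the fully-compliant analysis can remove patients from one arm only. It is therefore not a randomised comparison and is open to selection bias.

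The size rests on assumptions that the documents do not supply. It runs from nothing at zero correlation, through a slight effect at 90% compliance, to a roughly doubled false-positive rate at 70% compliance with correlation 0.5, and about 13% at 60%. The defect is confined to the second analysis. It should be corrected before analysis, because the rule is stated, can mislead, and has a better alternative that uses data largely already planned.

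**What to change.** 1. Name ITT as the sole confirmatory analysis.
2. As the estimate of effect when used, replace the compliant-only comparison with a complier-average effect that uses randomisation as the instrument. Take the ITT difference at the second sample (on the operating table, before skin prep), on the outcome scale the plan uses, for example mean count or a risk difference in culture positivity. Divide it by the between-arm difference in the share who started any part of the home regimen (shower or wipe) before that sample. Give a two-stage or bootstrap interval.
3. Define the treatment as the whole home regimen. Only the chlorhexidine arm is asked to shower, so assignment could change counts without a wipe. If only wipe use is recorded, state the assumption that the shower alone has no effect.
4. If the fully compliant subset is still shown, label it supportive and non-randomised, and adjust it for the office swab taken before the intervention. Do not divide the ITT effect by the two-wipe share. For example, if 90% start the regimen, 70% use both wipes, no control does either, and any use has the same effect E, the ITT effect is 0.9E. Dividing by 0.7 gives 1.29E, which credits partial users' benefit to full users.
5. Reconcile the placebo wording with the untreated control, say what compliance means for a control, and say whether a wipe used late in the pre-operative area counts as full compliance.

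Cost: plan wording and one calculation, plus a record of the pre-operative shower if that is not already collected. The downside is a wider interval than the naive subset comparison would give.
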